### **Statistical analysis:**

The Chi-Square test was used for comparison between the four groups within every follow up period, while marginal homogeneity test was used to compare the changes within each group per time.

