### **Null hypothesis**

The null hypothesis that will be tested in this project is that there would be no significant difference among the four tested restorative strategies at different clinical evaluation periods.

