#### **Eligibility criteria**

Participants were examined to form a group with 30 patients that justify the inclusion and exclusion criteria. Patients were required to have good general health, be older than 18 years old. Patients with extremely poor oral hygiene, severe or chronic periodontitis, or heavy bruxism habits will be excluded from the study.

Patients had to present at least four teeth with class II cavities to be restored (molars or premolar). Also, unsatisfactory class II restorations that are moderately deep with an adjacent tooth was involved.

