## **Interventions: Restorative procedures**

A split-mouth design was used in this study. For ormocer- based resin composite restorative system, it will be placed without resin flowable liner in one side, while it will be lined in the other side. The same protocol will be applied for methacrylate-based resin composite restorative system. Hence, each patient will receive four restorations with different strategies. All restorative procedures will be carried out by a single operator.

After administration of local anesthetic, rubber dam will be placed. The cavity preparation was then carried out with an outline limited to caries progression. The cavities depth in mm will be measured by a periodontal probe to give an idea about the thickness of the flowable composite liner (when used) and preserve 2 mm depth for the overlying resin. Restorative systems were then be applied according to the instructions recommended by their manufactures. Sectional pre-contoured matrix with ring, and wave like contour plastic wedges was used to restore the shape of the proximal walls. Adhesive and resin composites was cured using a LED (light

emitting diode) curing unit in the standard application mode and an output of 650 mW/cm^2.

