## Results:

Table: Scores of all tested criteria and results of Chi-Square and Marginal homogeneity tests

category	score	Baseline (n=30)				#	6 Months (n=30)				#	12 Months (n=30)				#	18 Months (n=30)				#	24 Months (n=30)				#	XF s	XB s	AFX s	AFB s
		XF	XB	AFX	AFB		XF	XB	AFX	AFB		XF	XB	AFX	AFB		XF	XB	AFX	AFB		XF	XB	AFX	AFB		XF s	XB s	AFX s	AFB s
Marginal staining	1	30	30	30	30	p=1.0	30	30	30	30	p=1.0	30	30	30	30	p=1.0	30	30	30	30	p=1.0	30	30	30	30	p=1.0	p1=1.0	p1=1.0	p1=1.0	p1=1.0
	2	0	0	0	0		0	0	0	0		0	0	0	0		0	0	0	0		0	0	0	0		p2=1.0	p2=1.0	p2=1.0	p2=1.0
	3	0	0	0	0		0	0	0	0		0	0	0	0		0	0	0	0		0	0	0	0		p3=1.0	p3=1.0	p3=1.0	p3=1.0
	4	0	0	0	0		0	0	0	0		0	0	0	0		0	0	0	0		0	0	0	0		p4=1.0	p4=1.0	p4=1.0	p4=1.0
	5	0	0	0	0		0	0	0	0		0	0	0	0		0	0	0	0		0	0	0	0					
Color match and translucency	1	28	29	30	30	p=0.288	28	29	30	30	p=0.288	28	29	30	30	p=0.288	28	29	30	30	p=0.288	28	29	30	30	p=0.288	p1=1.0	p1=1.0	p1=1.0	p1=1.0
	2	2	1	0	0		2	1	0	0		2	1	0	0		2	1	0	0		2	1	0	0		p2=1.0	p2=1.0	p2=1.0	p2=1.0
	3	0	0	0	0		0	0	0	0		0	0	0	0		0	0	0	0		0	0	0	0		p3=1.0	p3=1.0	p3=1.0	p3=1.0
	4	0	0	0	0		0	0	0	0		0	0	0	0		0	0	0	0		0	0	0	0		p4=1.0	p4=1.0	p4=1.0	p4=1.0
	5	0	0	0	0		0	0	0	0		0	0	0	0		0	0	0	0		0	0	0	0					
Fracture of material and retention	1	30	30	30	30	p=1.0	30	30	30	30	p=1.0	30	30	30	30	p=1.0	30	30	30	30	p=1.0	30	30	30	30	p=1.0	p1=1.0	p1=1.0	p1=1.0	p1=1.0
	2	0	0	0	0		0	0	0	0		0	0	0	0		0	0	0	0		0	0	0	0		p2=1.0	p2=1.0	p2=1.0	p2=1.0
	3	0	0	0	0		0	0	0	0		0	0	0	0		0	0	0	0		0	0	0	0		p3=1.0	p3=1.0	p3=1.0	p3=1.0
	4	0	0	0	0		0	0	0	0		0	0	0	0		0	0	0	0		0	0	0	0		p4=1.0	p4=1.0	p4=1.0	p4=1.0
	5	0	0	0	0		0	0	0	0		0	0	0	0		0	0	0	0		0	0	0	0					
Marginal adaptation	1	30	30	30	30	p=1.0	30	30	30	30	p=1.0	30	30	30	30	p=1.0	30	30	30	30	p=1.0	30	30	30	30	p=1.0	p1=1.0	p1=1.0	p1=1.0	p1=1.0
	2	0	0	0	0		0	0	0	0		0	0	0	0		0	0	0	0		0	0	0	0		p2=1.0	p2=1.0	p2=1.0	p2=1.0
	3	0	0	0	0		0	0	0	0		0	0	0	0		0	0	0	0		0	0	0	0		p3=1.0	p3=1.0	p3=1.0	p3=1.0
	4	0	0	0	0		0	0	0	0		0	0	0	0		0	0	0	0		0	0	0	0		p4=1.0	p4=1.0	p4=1.0	p4=1.0
	5	0	0	0	0		0	0	0	0		0	0	0	0		0	0	0	0		0	0	0	0					
Radiographic examination	1	30	30	30	30	p=1.0	30	30	30	30	p=1.0	30	30	30	30	p=1.0	30	30	30	30	p=1.0	30	30	30	30	p=1.0	p1=1.0	p1=1.0	p1=1.0	p1=1.0
	2	0	0	0	0		0	0	0	0		0	0	0	0		0	0	0	0		0	0	0	0		p2=1.0	p2=1.0	p2=1.0	p2=1.0
	3	0	0	0	0		0	0	0	0		0	0	0	0		0	0	0	0		0	0	0	0		p3=1.0	p3=1.0	p3=1.0	p3=1.0

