	4	0	0	0	0		0	0	0	0		0	0	0	0		0	0	0	0		0	0	0	0		p4=1.0	p4=1.0	p4=1.0	p4=1.0
	5	0	0	0	0		0	0	0	0		0	0	0	0		0	0	0	0		0	0	0	0					
Interproximal contact	1	30	30	30	30	p=1.0	30	30	30	30	p=1.0	30	30	30	30	p=1.0	30	30	30	30	p=1.0	29	28	27	28	p=0.784	p1=0.317	p1=0.317	p1=0.317	p1=0.317
	2	0	0	0	0		0	0	0	0		0	0	0	0		0	0	0	0		1	2	3	2		p2=0.157	p2=0.157	p2=0.157	p2=0.157
	3	0	0	0	0		0	0	0	0		0	0	0	0		0	0	0	0		0	0	0	0		p3=0.083	p3=0.083	p3=0.083	p3=0.083
	4	0	0	0	0		0	0	0	0		0	0	0	0		0	0	0	0		0	0	0	0		p4=0.157	p4=0.157	p4=0.157	p4=0.157
	5	0	0	0	0		0	0	0	0		0	0	0	0		0	0	0	0		0	0	0	0					
Postoperative (hyper-) sensitivity and tooth vitality	1	29	30	28	30	p=0.288	30	30	30	30	p=1.0	30	30	30	30	p=1.0	30	30	30	30	p=1.0	30	30	30	30	p=1.0	p1=0.317	p1=0.157	p1=0.083	p1=1.0
	2	1	0	2	0		0	0	0	0		0	0	0	0		0	0	0	0		0	0	0	0		p2=1.0	p2=1.0	p2=1.0	p2=1.0
	3	0	0	0	0		0	0	0	0		0	0	0	0		0	0	0	0		0	0	0	0		p3=0.157	p3=0.157	p3=0.157	p3=0.157
	4	0	0	0	0		0	0	0	0		0	0	0	0		0	0	0	0		0	0	0	0		p4=1.0	p4=1.0	p4=1.0	p4=1.0
	5	0	0	0	0		0	0	0	0		0	0	0	0		0	0	0	0		0	0	0	0					
Recurrent caries	1	30	30	30	30	p=1.0	30	30	30	30	p=1.0	30	30	30	30	p=1.0	30	30	30	30	p=1.0	30	30	30	30	p=1.0	p1=1.0	p1=1.0	p1=1.0	p1=1.0
	2	0	0	0	0		0	0	0	0		0	0	0	0		0	0	0	0		0	0	0	0		p2=1.0	p2=1.0	p2=1.0	p2=1.0
	3	0	0	0	0		0	0	0	0		0	0	0	0		0	0	0	0		0	0	0	0		p3=1.0	p3=1.0	p3=1.0	p3=1.0

	4	0	0	0	0		0	0	0	0		0	0	0	0		0	0	0	0		p4=1.0	p4=1.0	p4=1.0	p4=1.0
	5	0	0	0	0		0	0	0	0		0	0	0	0		0	0	0	0					
Tooth integrity (enamel cracks and tooth fractures)	1	30	30	30	30	p=1.0	30	30	30	30	p=1.0	30	30	30	30	p=1.0	30	30	30	30	p=1.0	p1=1.0	p1=1.0	p1=1.0	p1=1.0
	2	0	0	0	0		0	0	0	0		0	0	0	0		0	0	0	0		p2=1.0	p2=1.0	p2=1.0	p2=1.0
	3	0	0	0	0		0	0	0	0		0	0	0	0		0	0	0	0		p3=1.0	p3=1.0	p3=1.0	p3=1.0
	4	0	0	0	0		0	0	0	0		0	0	0	0		0	0	0	0		p4=1.0	p4=1.0	p4=1.0	p4=1.0
	5	0	0	0	0		0	0	0	0		0	0	0	0		0	0	0	0					

#USED test: Chi-Square test for comparing between groups (EXF, SDR and TNFBF) \$USED test: Marginal Homogeneity test for comparing between different follow up times as compared to baseline value

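### The plan gives only four-group chi-square p-values, with no estimate or interval for the matrix and liner questions, and prints p=1.0 where every restoration scores 1 and the test is undefined

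*Combined protocol and SAP*

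**What the plan says.** The between-group method is a single sentence under Statistical analysis: "The Chi-Square test was used for comparison between the four groups within every follow up period". A marginal homogeneity test covers change over time within each group. The section mentions no effect measure, confidence interval, margin, or rule for a comparison in which nobody has an event.

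The last paragraph of the Introduction sets two null hypotheses: matrix type has no effect on clinical performance, and a liner of the same category has no effect. The Null hypothesis section restates them as one four-group statement, that "there would be no significant difference among the four tested restorative strategies at different clinical evaluation periods".

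The results table, titled "Scores of all tested criteria and results of Chi-Square and Marginal homogeneity tests", lists nine criteria under five visits (baseline, 6, 12, 18 and 24 months), with 30 restorations per arm. It gives counts by score and p-values only. Wherever all four arms have 30 of 30 at score 1, the between-group entry is p=1.0.

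On design, the Interventions section says: "Hence, each patient will receive four restorations with different strategies". The sample is set under Eligibility criteria: "Participants were examined to form a group with 30 patients that justify the inclusion and exclusion criteria". No sample-size calculation is given.

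**The concern.** Both hypotheses are of the no-effect kind, and the only planned evidence on them is a set of omnibus p-values. A non-significant p-value does not say how large a difference remains possible. A four-group test also does not isolate either two-level contrast that the Introduction asks about.

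Most comparisons are at the ceiling of the scale, where the named test has no value. Printing p=1.0 there presents a placeholder as a test result, and p=1.0 is the value that looks most favourable to the null. What is at stake is the conclusion that the trial can support: a bare statement of non-significance, or a statement of how large a difference the data rule out.

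Interproximal contact shows why this matters. It is the only criterion whose scores have worsened by 24 months, and the Introduction itself says that the susceptibility of low-viscosity bulk-fill materials to proximal contact defects is unknown. The table offers only p=0.784 on it.

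**Working it through.** **Inputs.** Counts come from the results table. The arms are XF, XB, AFX and AFB. From the product names under Materials, I take XF and XB as methacrylate without and with liner, and AFX and AFB as ormocer without and with liner. The cut-off of score 2 or more is mine; the documents set none.

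**1. Reproduce the printed p-values.** Pearson chi-square = Σ(O − E)²/E on four arms by two scores, 3 degrees of freedom.
- "Color match and translucency", score 1 in 28/29/30/30: expected 29.25 and 0.75 per arm. Squared deviations sum to 1.5625 + 0.0625 + 0.5625 + 0.5625 = 2.75. Chi-square = 2.75/29.25 + 2.75/0.75 = 3.761, p = 0.288, as printed.
- "Postoperative (hyper-) sensitivity and tooth vitality" at baseline, 29/30/28/30: the same counts in another order, so p = 0.288, as printed.
- Interproximal contact at 24 months, 29/28/27/28: expected 28 and 2. Squared deviations sum to 2. Chi-square = 2/28 + 2/2 = 1.071, p = 0.784, as printed.

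The test used is therefore the ordinary Pearson test.

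**2. Apply it to 30/30/30/30.** Expected counts are 30 for score 1 and 0 for every other score, so each other score contributes 0/0. If the empty rows are dropped, the degrees of freedom are (1 − 1)(4 − 1) = 0. There is no p-value to report.

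**3. Count such comparisons.** Those with any variation are colour match (5 visits), contact (1) and sensitivity (1), 7 in all.
- By table layout: 9 × 5 = 45, and 45 − 7 = 38.
- Legible: "Tooth integrity (enamel cracks and tooth fractures" shows four of its five visit blocks in the text available, probably a reading loss, so 44 − 7 = 37.
- Clinical evaluation lists only baseline, 12 and 24 months: 9 × 3 = 27. Those with variation are 3 + 1 + 1 = 5, so 27 − 5 = 22.

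**4. What zero events leave open.**
- One arm, 0/30: exact two-sided 95% upper limit 1 − 0.025^(1/30) = 0.1157, or 11.6%.
- Two arms, 0/30 against 0/30: the Wilson upper limit is z²/(n + z²) = 3.841/33.841 = 0.1135. The Newcombe interval for the difference is then ±11.4 points.
- Patient as the unit: a patient's matrix or liner difference lies between −1 and 1, and is zero unless that patient has an event. The mean difference therefore cannot exceed the proportion of patients with any event. With 0 of 30 patients, that is bounded at 11.6%, whatever the correlation within patients.

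**5. Contact at 24 months** (score 2 in 1, 2, 3 and 2 of 30 for XF, XB, AFX and AFB), Newcombe 95% intervals:

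| Contrast | Counts | Difference (points) | 95% interval |
|---|---|---|---|
| AFX vs XF | 3/30 vs 1/30 | 6.7 | −8.2 to 22.5 |
| Ormocer vs methacrylate | 5/60 vs 3/60 | 3.3 | −6.6 to 13.6 |
| Lined vs unlined | 4/60 vs 4/60 | 0.0 | −10.1 to 10.1 |

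These intervals ignore that each patient contributes to every arm, because the within-patient cross-tabulation is not shown. They illustrate scale only.

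**The case against.** The other side has a fair case. The table prints every count, so 30/30/30/30 stands beside each p=1.0 and the ceiling is visible. An exact conditional test on a table with only one possible arrangement returns p = 1, so the null is not rejected under either label. The documents define no event and no margin, so they offer no benchmark for calling 11 points large. The illustrative intervals do not respect the split-mouth design. The arm labels are inferred, and the table footnote names other groups.

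Most of this stands. Relabelling p=1.0 alone corrects reporting and changes no decision. The substance lies in the missing estimates and intervals, which affects the seven computable comparisons equally. Printed counts do not fill that gap, because a reader cannot recover within-patient differences from them.

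Two stronger readings are tempting. One is that the zero-event cells carry no information. They do carry some: 0/30 bounds the event rate at 11.6%. The other is that the trial declares the four strategies equal. No sentence in the documents interprets these p-values, and the Null hypothesis section speaks of no significant difference, which is not an equivalence claim. The risk is in how p=1.0 may be read, not in a conclusion already drawn.

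**Conclusion.** The point holds in this form. The plan provides no estimate or interval for the matrix and liner questions, and the p=1.0 entries cannot be results of the test it names. The number affected is 38 of 45 by table layout, which is partly inferred; 37 of 44 are legible, and 22 of 27 fall on the three visits listed under Clinical evaluation. On each count more than 80% of the between-group entries are not test results (38/45 = 84%, 37/44 = 84%, 22/27 = 81%).

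In those cells no test is possible, and differences of roughly 11 points between two arms are not excluded. This rests on a two-sided 95% level, which the documents do not state, on a cut-off at score 2 or more, and on all 30 patients contributing one restoration per arm. The difference intervals are unpaired and illustrative; the 11.6% patient-level bound does not depend on the pairing.

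**What to change.** - In the Statistical analysis section and the table, replace p=1.0 by *no events, not testable* wherever no restoration scores above 1.
- For each criterion at 24 months, report the number scoring 2 or more in each arm.
- Report the risk difference for ormocer against methacrylate and for lined against unlined, each with a 95% interval that treats the patient as the unit. Each patient has two restorations per level, so an ordinary matched-pair interval does not fit directly. One option is to take, for each patient, the proportion of the two restorations at one level scoring 2 or more, subtract the same proportion at the other level, and analyse the 30 differences. A patient-clustered method is another.
- Where there are no events, give the exact upper limit based on 30 patients (11.6%).
- Results already exist, so label the analysis and the score cut-off as post hoc.
- Word the conclusion as the largest difference not excluded.

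The cost is a little more analysis on data already held, some table edits, and a less favourable-sounding conclusion. No visit or procedure changes.

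### The within-group marginal homogeneity p-values are uncorrected large-sample values on 1 to 3 changed pairs out of 30; small-sample versions give larger values, about threefold for the exact conditional test, though no conclusion changes.

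*Combined protocol and SAP*

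**What the plan says.** The Statistical analysis section gives the within-group method in one clause: "marginal homogeneity test was used to compare the changes within each group per time". The Results table footnote adds that the comparisons are with baseline: "Marginal Homogeneity test for comparing between different follow up times as compared to baseline value". Neither place says whether the test is asymptotic or exact. The section states no significance level, sidedness or rule for small counts.

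Two criteria in the Results table have score distributions that differ from baseline at some visit.

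- **Interproximal contact.** All 30 restorations per strategy score 1 at baseline. At 24 months the score-1 counts for XF, XB, AFX and AFB, with the between-strategy p-value, are "29 28 27 28 p=0.784".
- **Postoperative sensitivity.** The score-1 counts at baseline are "29 30 28 30 p=0.288". All 30 per strategy score 1 from 6 months on.

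The within-group p-values printed for these rows are 0.317, 0.157, 0.083 and 1.0. All other criteria show 1.0 throughout.

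**The concern.** Each patient contributes one restoration per strategy, so each comparison of a visit with baseline rests on 30 pairs. In a paired test of this kind only pairs whose score changed carry information, and here there are 1 to 3 of them. A normal approximation to a sign test on 1 to 3 observations has no large-sample justification. One change out of one is the least extreme result possible, yet it is printed as 0.317. Three changes cannot give an exact two-sided p below 0.25, yet 0.083 is printed.

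What is at stake is how the evidence reads. Interproximal contact is the only criterion in the table that worsens from baseline, and the Introduction raises proximal contact defects with low-viscosity bulk-fill material as an open question. A reader could take 0.083 as a near-significant loss of contact. A bare p-value also hides how much deterioration 30 restorations leave open.

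**Working it through.** **Inputs (Results table).** There are 30 pairs per strategy and only scores 1 and 2 occur. In both affected rows one of the two margins is 30/30 at score 1, so the counts fix the number of changed pairs k, and all changes go one way.

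- Contact, baseline to 24 months: k = 30 − 29, 30 − 28, 30 − 27, 30 − 28 = 1, 2, 3, 2 for XF, XB, AFX, AFB.
- Sensitivity, baseline to any later visit: k = 30 − 29, 30 − 30, 30 − 28, 30 − 30 = 1, 0, 2, 0.

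**Formulas.** With two occupied categories the marginal homogeneity test reduces to McNemar's test. For k one-way changes:

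- uncorrected large-sample: z = k/√k = √k, p = 2(1 − Φ(√k));
- continuity-corrected: χ² = (k − 1)²/k on 1 degree of freedom;
- exact conditional: p = min(1, 2 × 0.5^k);
- mid-p: exact p minus the probability of the observed outcome, which is 0.5^k here.

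**Reproducing the printed values, then the alternatives.**

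| k | Printed | Large-sample | Continuity-corrected | Exact | Mid-p | Exact ÷ large-sample | Mid-p ÷ large-sample |
|---|---|---|---|---|---|---|---|
| 1 | 0.317 | 0.3173 | 1.000 | 1.000 | 0.500 | 3.15 | 1.58 |
| 2 | 0.157 | 0.1573 | 0.480 | 0.500 | 0.250 | 3.18 | 1.59 |
| 3 | 0.083 | 0.0833 | 0.248 | 0.250 | 0.125 | 3.00 | 1.50 |

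Only the uncorrected large-sample form reproduces the printed figures. An unconditional exact test (the same statistic, maximised over the unknown rate of change) gives about 0.54, 0.22 and 0.10. The printed values are below every small-sample reference tried.

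**Interval.** The Clopper-Pearson limits for x changes out of 30 are the 0.025 quantile of Beta(x, 31 − x) and the 0.975 quantile of Beta(x + 1, 30 − x). For AFX contact, 3/30 = 10% (2.1% to 26.5%).

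**Error rate at an assumed two-sided 5% level.** Given k changed pairs, the large-sample rule rejects with probability 0 at k = 1, 2 and 3, 12.5% at 4, 6.25% at 5, 3.1% at 6, 1.6% at 7, 7.0% at 8, 3.9% at 9 and 2.2% at 10. Since k is random, these are averaged over a Binomial(30, q) distribution, where q is the true rate of changed pairs. The overall size is 0.2%, 1.4% and 3.1% at q = 1/30, 2/30 and 3/30. It stays below 5% up to q = 50% and peaks at 5.4% near q = 84%. At the same three low rates the exact conditional test has size 0.0% to 0.2%.

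**Labels.** The match above is between k and the set of printed values, not cell by cell. In the contact row all four strategy columns repeat 0.317, 0.157, 0.083, 0.157 as p1 to p4. That sequence follows the 24-month changes of XF, XB, AFX and AFB in order. It does not fit four successive visits, because nothing changed before 24 months. In the sensitivity row XB shows p1 = 0.157 with no change and AFX shows p1 = 0.083 with two changes.

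**The case against.** The case against acting has several parts.

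**Error rate.** A reader might infer that the test as run rejects too often. The conditional rates at 4, 5 and 8 changes suggest this, but they are selected values; at 1 to 3 changes the rule cannot reject at 5%, and the overall size is not materially above nominal. This objection stands.

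**One more event.** A reader might also infer that a fourth change in AFX would have been called significant, because four one-way changes give 0.0455 against an exact 0.125. That case is hypothetical: the 24-month data are complete, and the documents state no 0.05 rule.

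**Role of the test.** The null hypotheses in the Introduction and in the Null hypothesis section are all between-strategy. No section lets a within-group p-value decide whether a strategy has deteriorated. This too stands and limits the importance of the point.

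**Choice of reference.** The factor of 3 depends on taking the exact conditional test, which is conservative. Against mid-p it is about 1.5, and against the unconditional exact test smaller still at three changes (0.10 against 0.083). This stands as a limit on the size of the discrepancy; its direction is the same throughout.

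**Other rows.** Margins do not fix k everywhere. XF colour match is 28 and 2 at every visit, which would allow up to four offsetting changes. Equal margins give p = 1 under the large-sample and exact forms alike, so these cells are unaffected.

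**Conclusion.** The point holds as one of reporting accuracy. The printed 0.317, 0.157 and 0.083 are large-sample p-values used where that approximation is unreliable. The exact conditional values are 3.0 to 3.2 times larger and the mid-p values 1.5 to 1.6 times larger, so the evidence of change is overstated.

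No conclusion flips: every within-group value exceeds 0.05 under any version considered, with 0.05 taken as a conventional assumption. The documents do not support reading this as general inflation of the type I error or as a threat to the between-strategy hypotheses.

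The calculation assumes that the tabulated counts are right, that each patient supplies one restoration per strategy, and that tests are two-sided. It does not assume that any particular p-value sits in its correct column. The misaligned labels are a separate defect, but the same re-run can settle both.

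**What to change.** - In the Statistical analysis section, specify a small-sample version of the within-group test: exact marginal homogeneity (exact McNemar where only scores 1 and 2 occur), or mid-p as a less conservative choice. State the significance level and sidedness.
- Recompute the interproximal contact and sensitivity cells. Beside each p-value print the number changed out of 30, the direction and an exact 95% interval, for example AFX contact at 24 months: 3/30 = 10% (2.1% to 26.5%), exact p = 0.25.
- Define p1 to p4 and realign them with strategy columns and visits.
- Present any four-change illustration or conditional false-positive rate only if it is labelled as hypothetical and conditional.

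The cost is one or two sentences and a re-run of two rows. The downside is larger p-values and, with the exact conditional test, very little chance of rejecting at the change rates seen here. The interval should therefore carry the interpretation.

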## Results:

Table: Scores of all tested criteria and results of Chi-Square and Marginal homogeneity tests

category	score	Baseline (n=30)				#	6 Months (n=30)				#	12 Months (n=30)				#	18 Months (n=30)				#	24 Months (n=30)				#	XF s	XB s	AFX s	AFB s
		XF	XB	AFX	AFB		XF	XB	AFX	AFB		XF	XB	AFX	AFB		XF	XB	AFX	AFB		XF	XB	AFX	AFB		XF s	XB s	AFX s	AFB s
Marginal staining	1	30	30	30	30	p=1.0	30	30	30	30	p=1.0	30	30	30	30	p=1.0	30	30	30	30	p=1.0	30	30	30	30	p=1.0	p1=1.0	p1=1.0	p1=1.0	p1=1.0
	2	0	0	0	0		0	0	0	0		0	0	0	0		0	0	0	0		0	0	0	0		p2=1.0	p2=1.0	p2=1.0	p2=1.0
	3	0	0	0	0		0	0	0	0		0	0	0	0		0	0	0	0		0	0	0	0		p3=1.0	p3=1.0	p3=1.0	p3=1.0
	4	0	0	0	0		0	0	0	0		0	0	0	0		0	0	0	0		0	0	0	0		p4=1.0	p4=1.0	p4=1.0	p4=1.0
	5	0	0	0	0		0	0	0	0		0	0	0	0		0	0	0	0		0	0	0	0					
Color match and translucency	1	28	29	30	30	p=0.288	28	29	30	30	p=0.288	28	29	30	30	p=0.288	28	29	30	30	p=0.288	28	29	30	30	p=0.288	p1=1.0	p1=1.0	p1=1.0	p1=1.0
	2	2	1	0	0		2	1	0	0		2	1	0	0		2	1	0	0		2	1	0	0		p2=1.0	p2=1.0	p2=1.0	p2=1.0
	3	0	0	0	0		0	0	0	0		0	0	0	0		0	0	0	0		0	0	0	0		p3=1.0	p3=1.0	p3=1.0	p3=1.0
	4	0	0	0	0		0	0	0	0		0	0	0	0		0	0	0	0		0	0	0	0		p4=1.0	p4=1.0	p4=1.0	p4=1.0
	5	0	0	0	0		0	0	0	0		0	0	0	0		0	0	0	0		0	0	0	0					
Fracture of material and retention	1	30	30	30	30	p=1.0	30	30	30	30	p=1.0	30	30	30	30	p=1.0	30	30	30	30	p=1.0	30	30	30	30	p=1.0	p1=1.0	p1=1.0	p1=1.0	p1=1.0
	2	0	0	0	0		0	0	0	0		0	0	0	0		0	0	0	0		0	0	0	0		p2=1.0	p2=1.0	p2=1.0	p2=1.0
	3	0	0	0	0		0	0	0	0		0	0	0	0		0	0	0	0		0	0	0	0		p3=1.0	p3=1.0	p3=1.0	p3=1.0
	4	0	0	0	0		0	0	0	0		0	0	0	0		0	0	0	0		0	0	0	0		p4=1.0	p4=1.0	p4=1.0	p4=1.0
	5	0	0	0	0		0	0	0	0		0	0	0	0		0	0	0	0		0	0	0	0					
Marginal adaptation	1	30	30	30	30	p=1.0	30	30	30	30	p=1.0	30	30	30	30	p=1.0	30	30	30	30	p=1.0	30	30	30	30	p=1.0	p1=1.0	p1=1.0	p1=1.0	p1=1.0
	2	0	0	0	0		0	0	0	0		0	0	0	0		0	0	0	0		0	0	0	0		p2=1.0	p2=1.0	p2=1.0	p2=1.0
	3	0	0	0	0		0	0	0	0		0	0	0	0		0	0	0	0		0	0	0	0		p3=1.0	p3=1.0	p3=1.0	p3=1.0
	4	0	0	0	0		0	0	0	0		0	0	0	0		0	0	0	0		0	0	0	0		p4=1.0	p4=1.0	p4=1.0	p4=1.0
	5	0	0	0	0		0	0	0	0		0	0	0	0		0	0	0	0		0	0	0	0					
Radiographic examination	1	30	30	30	30	p=1.0	30	30	30	30	p=1.0	30	30	30	30	p=1.0	30	30	30	30	p=1.0	30	30	30	30	p=1.0	p1=1.0	p1=1.0	p1=1.0	p1=1.0
	2	0	0	0	0		0	0	0	0		0	0	0	0		0	0	0	0		0	0	0	0		p2=1.0	p2=1.0	p2=1.0	p2=1.0
	3	0	0	0	0		0	0	0	0		0	0	0	0		0	0	0	0		0	0	0	0		p3=1.0	p3=1.0	p3=1.0	p3=1.0
	4	0	0	0	0		0	0	0	0		0	0	0	0		0	0	0	0		0	0	0	0		p4=1.0	p4=1.0	p4=1.0	p4=1.0
	5	0	0	0	0		0	0	0	0		0	0	0	0		0	0	0	0		0	0	0	0					
Interproximal contact	1	30	30	30	30	p=1.0	30	30	30	30	p=1.0	30	30	30	30	p=1.0	30	30	30	30	p=1.0	29	28	27	28	p=0.784	p1=0.317	p1=0.317	p1=0.317	p1=0.317
	2	0	0	0	0		0	0	0	0		0	0	0	0		0	0	0	0		1	2	3	2		p2=0.157	p2=0.157	p2=0.157	p2=0.157
	3	0	0	0	0		0	0	0	0		0	0	0	0		0	0	0	0		0	0	0	0		p3=0.083	p3=0.083	p3=0.083	p3=0.083
	4	0	0	0	0		0	0	0	0		0	0	0	0		0	0	0	0		0	0	0	0		p4=0.157	p4=0.157	p4=0.157	p4=0.157
	5	0	0	0	0		0	0	0	0		0	0	0	0		0	0	0	0		0	0	0	0					
Postoperative (hyper-) sensitivity and tooth vitality	1	29	30	28	30	p=0.288	30	30	30	30	p=1.0	30	30	30	30	p=1.0	30	30	30	30	p=1.0	30	30	30	30	p=1.0	p1=0.317	p1=0.157	p1=0.083	p1=1.0
	2	1	0	2	0		0	0	0	0		0	0	0	0		0	0	0	0		0	0	0	0		p2=1.0	p2=1.0	p2=1.0	p2=1.0
	3	0	0	0	0		0	0	0	0		0	0	0	0		0	0	0	0		0	0	0	0		p3=0.157	p3=0.157	p3=0.157	p3=0.157
	4	0	0	0	0		0	0	0	0		0	0	0	0		0	0	0	0		0	0	0	0		p4=1.0	p4=1.0	p4=1.0	p4=1.0
	5	0	0	0	0		0	0	0	0		0	0	0	0		0	0	0	0		0	0	0	0					
Recurrent caries	1	30	30	30	30	p=1.0	30	30	30	30	p=1.0	30	30	30	30	p=1.0	30	30	30	30	p=1.0	30	30	30	30	p=1.0	p1=1.0	p1=1.0	p1=1.0	p1=1.0
	2	0	0	0	0		0	0	0	0		0	0	0	0		0	0	0	0		0	0	0	0		p2=1.0	p2=1.0	p2=1.0	p2=1.0
	3	0	0	0	0		0	0	0	0		0	0	0	0		0	0	0	0		0	0	0	0		p3=1.0	p3=1.0	p3=1.0	p3=1.0

	4	0	0	0	0		0	0	0	0		0	0	0	0		0	0	0	0		p4=1.0	p4=1.0	p4=1.0	p4=1.0
	5	0	0	0	0		0	0	0	0		0	0	0	0		0	0	0	0					
Tooth integrity (enamel cracks and tooth fractures)	1	30	30	30	30	p=1.0	30	30	30	30	p=1.0	30	30	30	30	p=1.0	30	30	30	30	p=1.0	p1=1.0	p1=1.0	p1=1.0	p1=1.0
	2	0	0	0	0		0	0	0	0		0	0	0	0		0	0	0	0		p2=1.0	p2=1.0	p2=1.0	p2=1.0
	3	0	0	0	0		0	0	0	0		0	0	0	0		0	0	0	0		p3=1.0	p3=1.0	p3=1.0	p3=1.0
	4	0	0	0	0		0	0	0	0		0	0	0	0		0	0	0	0		p4=1.0	p4=1.0	p4=1.0	p4=1.0
	5	0	0	0	0		0	0	0	0		0	0	0	0		0	0	0	0					

#USED test: Chi-Square test for comparing between groups (EXF, SDR and TNFBF) \$USED test: Marginal Homogeneity test for comparing between different follow up times as compared to baseline value

